7.4 Grading of Adverse Events

Allergic reactions will be graded according to the CoFAR Grading System for Allergic Reactions, with additional modification to Grade 1 symptoms as shown in Table 8.

Grade 1 - Transient	Grade 1 – Mild	Grade 2 – Moderate	Grade 3 – Severe	Grade 4 – Life Threatening	Grade 5 Death
Transient mild discomfort (< 48 hours). (<20mins). No limitation in activity	Mild discomfort (< 48 hours). No limitation in activity	Symptoms produce mild to moderate limitation in activity.	Marked limitation in activity.	Extreme limitation in activity.	Death
No assistance or medical intervention / therapy required.	No assistance or medical intervention/ therapy required.	Some assistance may be needed; no or minimal intervention/ therapy is required. Hospitalization is possible but unlikely.	Assistance usually required; Medical intervention is required (Parenteral medication(s) are usually indicated)	Significant assistance and medical intervention is required; hospitalisation is probable.	
Symptoms may include pruritus, periorbital or facial angioedema, swelling or rash, mild abdominal discomfort, or other transient symptoms.		Symptoms may include persistent hives, wheezing without dyspnea, abdominal discomfort / increased vomiting, or other symptoms	Symptoms may include bronchospasm with dyspnoea, severe abdominal pain, throat tightness with hoarseness, transient hypotension among others.	Symptoms may include persistent hypotension and/or hypoxia with resultant decreased level of consciousness associated with collapse and/ or incontinence or other life- threatening symptoms.	

Table 8: CoFAR Specific Grading System for Allergic Reactions

7.5 Safety Monitoring Plan

The PI will perform regular data and safety monitoring. Safety data including side effects and adverse reactions will be monitored from time of enrolment to completion of study. The PI will report AE/ SAE to CIRB as per guidelines stipulated above.

7.6 Complaint Handling

Complaints will be handled by the PI and dealt with according to the institution's guidelines.

8 DATA ANALYSIS

8.1 Data Quality Assurance

The PI and co-I (at least 2 persons) will independently and regularly check each other's data collection forms, data entry, to ensure accurate and complete data collection and data entry, in accordance to the protocol. Any disagreements will be discussed together with the third co-I for consensus.

8.2 Data Entry and Storage

Data will be first entered into hardcopy data collection forms (DCF). These forms will be stored under lock and key in access-controlled Paediatric office, only accessible to the study team. Data will then be transcribed from DCF to electronic forms (Microsoft Excel/ SPSS). Coded data will be stored on password-protected files on password-protected computers' shared folders, and all identifying information will only be available to the researchers in a file separate from the coded data that is also password-protected.

9 SAMPLE SIZE AND STATISTICAL METHODS

9.1 Determination of Sample Size

The incidence of natural resolution of egg allergy over 12 month period is about 15% (4),(10). The efficacy for desensitisation using raw/cooked eggs is about 80% (ranging between 55% -100%) whilst that for OIT using baked egg products is about 50%. As there are no prior studies using pancake to desensitise egg-allergic patients, we are estimating the efficacy to be in between that of raw/cooked eggs and baked eggs, at about 65%. We plan to recruit 33 egg-allergic children to the study, who will be randomised 2:1 to active (n=22) or control (n=11) groups. This will allow us to detect a difference in rates of desensitisation of 50%, with 80% power using a two-sided significance level of 0.05, whilst allowing for a 30% attrition rate. Sample size calculation was performed using PASS 14 (Power Analysis and Sample Size Software (2015). NCSS, LLC. Kaysville, Utah, USA, [ncss.com/software/pass.](http://ncss.com/software/pass/)).

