The BER group who tolerate at least 3mg of muffin in the baseline baked egg FC will undergo initial escalation with cookies in hospital (T1C). The first dose to be administered during the initial escalation will be individualised based on the outcomes of the baseline baked egg FC while the home starting dose will be the last dose tolerated during initial escalation. The starting cookie dose will be administered daily at home for a minimum of 2 weeks. Subsequent updosings will be done at home on a 2-weekly basis. When participants have successfully reached the target dose (Table 6 Step 11), they will remain on this dose for a minimum of 2 weeks before undergoing pancake initial escalation to begin pancake OIT (T2P). Those reacting at 37.5mg or 75mg will not begin OIT with pancakes but instead resume cookie OIT Step 11 for another minimum 4 weeks before re-attempting pancake initial escalation.

All participants who have completed at least 16 weeks of maintenance pancake OIT will undergo an open cooked egg FC at the end of treatment to assess for desensitisation (T3). Participants who tolerate 4443mg of cooked egg and deemed successfully desensitised will then stop OIT for approximately 6-8 weeks prior to returning for a repeat cooked egg FC to assess for sustained unresponsiveness (T4).

Participants who tolerate 4443mg of cooked egg at SU FC will be allowed ad libitum cooked egg consumption post study. Participants who develop allergic reactions at SU FC will resume previous maintenance dose.

Control subjects will receive the current best standard care, i.e. strict egg avoidance with provision of rescue medication and training. They will then undergo an open cooked egg FC between 12 and 18 months to assess for cooked egg tolerance.

Approximate time to complete study recruitment is 12 months. Total OIT duration from initial escalation to desensitisation FC is a minimum of 12 months and maximum of 18 months.

[figure not shown]

Figure 1: POET Study Design

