4.3.2.6 Desensitisation (DS) Open Food Challenge (T3)

All participants who have completed at least 16 weeks of maintenance pancake OIT (Table 5 Step 7) will undergo an open cooked egg challenge at the end of treatment (T3) to assess for desensitisation. This is subjected to a total OIT duration (from initial escalation to exit challenge) of a minimum 12 months and maximum 18 months. All control subjects will undergo an open cooked egg challenge between 12 and 18 months (T3).

Desensitisation Open Food Challenge to Cooked Egg		
Dose	Egg Protein (mg)	Equivalent serving of cooked egg (g)
1	3	0.02
2	10	0.08
3	30	0.24
4	100	0.8
5	300	2.4
6	1000	8
7	3000	24
Cumulative dose		35.54

Table 7: Dosing protocol for DS Open FC to cooked egg

Successful desensitisation is defined as passing the FC to cooked egg, tolerating 4443mg of egg protein.

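### Section 9.1 states 80% power, but the planned Fisher's exact test gives 75.4% at 22/11 and 54.8% after 30% attrition, and the 15% control rate is a 12-month figure for a 12 to 18 month endpoint

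*Combined protocol and SAP*

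**What the plan says.** Section 9.1 gives the control rate as follows: "The incidence of natural resolution of egg allergy over 12 month period is about 15" per cent. For the active arm it says "we are estimating the efficacy to be in between that of raw/cooked eggs and baked eggs, at about 65" per cent, and attaches no time point. The size and split are given as "We plan to recruit 33 egg-allergic children to the study, who will be randomised 2:1 to active (n=22) or control (n=11) groups". The claim is that this will "detect a difference in rates of desensitisation of 50%, with 80% power using a two-sided significance level of 0.05". Losses are covered by a further clause: "whilst allowing for a 30% attrition rate". The section names the software but not the formula or test used for sizing.

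Section 9.2.1 makes a two-sided Fisher's exact test the primary analysis. On timing, section 4.3.2.6 says "All control subjects will undergo an open cooked egg challenge between 12 and 18 months (T3", and sections 1.2.2 and 4 give controls the same window. For the active arm, section 4 says "Total OIT duration from initial escalation to desensitisation FC is a minimum of 12 months and maximum of 18 months".

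**The concern.** Two inputs to the power statement need checking against the rest of the plan.

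- **The test.** Fisher's exact test is conservative in small samples. A size derived from a large-sample formula can fall well short when this test is used on about 8 to 11 controls.
- **The horizon.** The control rate covers 12 months, while the control endpoint is read at 12 months at the earliest and 18 at the latest. Section 9.1 makes no adjustment. If children keep outgrowing the allergy after month 12, the control rate at the challenge will exceed 15%.

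At stake is the credibility of the 80%. Someone weighing a non-significant result would use that figure to judge how much it says against the treatment.

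**Working it through.** **Inputs.** From section 9.1: control 15%, active 65%, two-sided 0.05, 80% power, 2:1 allocation, 33 children (22/11), 30% attrition. From section 9.2.1: Fisher's exact test. From sections 1.2.2, 4 and 4.3.2.6: challenge at 12 to 18 months.

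**Step 1: reproduce the 33.** Normal approximation with unpooled variance:

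n(control) = (1.960 + 0.842)² × [0.15×0.85 + 0.65×0.35/2] / 0.50² = 7.57

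The total is 3 × 7.57 = 22.7, rounded to 23, and 23/0.70 gives 33. By arm, 7.57/0.70 gives 11 and 15.15/0.70 gives 22. Approximate power at 15 active and 8 control is 80.9%. So the stated size and power follow from the plan's own inputs under this formula.

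The other variants tried do not give 33 once attrition is included:

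| Method | Total before attrition | Total after 30% attrition |
|---|---|---|
| Unpooled normal | 23 | 33 |
| Pooled normal | 33 | 48 |
| Continuity-corrected | 42 | 61 |
| Exact Fisher | 36 | 52 |

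**Step 2: power of the planned test.** Power is the sum, over all pairs of outcomes (x of n control, y of m active), of the product of the two binomial probabilities wherever the two-sided Fisher p-value is at most 0.05. At 65% versus 15%:

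- 22/11: 75.4%
- 15/8: 54.8%

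**Step 3: the 12 to 18 month window.** The documents give no resolution rate beyond 12 months. *Assumption:* constant hazard, so the control rate at month t is 1 − 0.85^(t/12).

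- Month 15: 1 − 0.85^1.25 = 18.4%
- Month 18: 1 − 0.85^1.5 = 21.6%

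The active arm is treated in two ways:

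- (a) Held at 65%. The difference is 50, 46.6 and 43.4 points at 12, 15 and 18 months.
- (b) Active non-responders resolve at the same extra rate as controls. Among controls unresolved at month 12, the extra share is (18.4 − 15)/85 = 4.0% by month 15 and (21.6 − 15)/85 = 7.8% by month 18. The active rate becomes 65 + 35 × 0.040 = 66.4% and 65 + 35 × 0.078 = 67.7%, so the difference is 48.0 and 46.1 points.

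Exact Fisher power, if every child is challenged at the month shown:

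| Month | Control rate | (a) 22/11 | (a) 15/8 | (b) 22/11 | (b) 15/8 |
|---|---|---|---|---|---|
| 12 | 15.0% | 75.4% | 54.8% | 75.4% | 54.8% |
| 15 | 18.4% | 66.6% | 48.2% | 69.3% | 51.6% |
| 18 | 21.6% | 57.8% | 42.1% | 63.5% | 48.7% |

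**Step 4: which cause is larger.** At 15/8, going from the stated 80% to 54.8% loses 25.2 points, with the control rate at exactly 15%. This part is due to the test. Going from 54.8% to 42.1% loses a further 12.7 points, and only in the worst timing case.

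**The case against.** The strongest reply concerns timing. A reader might infer that the horizon alone makes the 50-point difference and the 80% incompatible with the design, or that the plan's own annual rate puts the control rate at 18-22%. The documents do not support either reading.

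- Month 12 lies inside the permitted window, so 15% fits controls challenged at its start.
- Section 9.1 gives a 12-month figure, not an annual rate that continues. Section 1.1 describes tolerance being acquired through childhood, but section 1.2.3 notes the belief that children above 4-5 years are less likely to outgrow the allergy, and enrolment runs from 2 to 15 years. Constant hazard is therefore an assumption made here.
- Both arms share the window and the 65% is undated. If the 50-point gap held at every month, Fisher power at 22/11 would be 75.4%, 73.0% and 71.5%, and at 15/8 it would be 54.8%, 56.5% and 58.1%. Holding the gap is not the natural default, however. By month 18 the active rate would have to reach 71.6%, so about 19% of the remaining 35% would have to resolve (6.6/35), against 7.8% of unresolved controls.

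These points stand, and they make the timing part conditional. They do not touch Step 2, which uses the plan's own 15% and 65%.

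It can also be said that the primary analysis is by intention to treat (section 9.2), so 15/8 is too harsh. Section 9.2 does not say how a missing challenge is counted. If the 30% lost were kept as failures in both arms, the rates would be 0.70 × 65 = 45.5% and 0.70 × 15 = 10.5%, and Fisher power at 22/11 would be 44.4%, lower still. Only with complete outcomes does 75.4% apply, and that too is below 80%.

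**Conclusion.** The stated 80% is wrong for the planned analysis. With section 9.1's own rates, Fisher's exact test has 75.4% power with no attrition and 54.8% with the 30% attrition that the section says it has allowed for. This needs no outside figure. It takes 15/8 as the evaluable split after attrition.

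The horizon mismatch is real but secondary. The 15% is the most favourable control rate in the 12 to 18 month window if resolution continues. Its cost cannot be fixed from the documents. Under constant hazard, with all children challenged at month 18, power is 57.8% to 63.5% at 22/11 and 42.1% to 48.7% at 15/8. The lower figures hold the active arm at 65%, and the higher ones let its non-responders resolve at the control rate. Correcting only the control rate would leave the larger part of the shortfall in place.

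**What to change.** Reword section 9.1 and leave enrolment at 33:

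1. Name the method behind the 33.
2. Replace the 80% with the power of the two-sided Fisher's exact test, at 22/11 and after 30% attrition (75.4% and 54.8% at 65% versus 15%).
3. Show that power over a range of control rates, for example 15-22%, to reflect the 12 to 18 month challenge window. Label the range as an assumption and say what is assumed for the active arm over the same months.

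This changes text only: no visit, treatment or recruitment target is affected. The downside is that the stated power becomes less favourable.

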9.2 Statistical and Analytical Plans

The primary analysis will be performed on an intention to treat basis: all subjects allocated to each arm will be analysed together as representing that treatment arm, irrespective of compliance and whether or not they have completed the prescribed regimen. A secondary

analysis will also be performed on a per protocol basis. Statistical analysis was performed using SAS software version 9.4 for Windows (Cary, NC: SAS Institute Inc.). Statistical significant is set at $p < 0.05$.

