9.2.1 Analysis of Primary Outcome

The primary analysis will compare the proportion of subjects who can tolerate 4443mg or more of egg protein in the active and control groups, using a two-sided Fisher's exact test.

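### The 80% power in section 9.1 does not hold for the Fisher's exact test planned in 9.2.1: at the stated rates it is 75% with all 33 children and about 55% after 30% attrition

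*Combined protocol and SAP*

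**What the plan says.** Section 9.1 (Determination of Sample Size) assumes about 15% natural resolution over 12 months in controls and about 65% desensitisation on pancake oral immunotherapy. It plans 33 children randomised 2:1, 22 active and 11 control. Of this number it says: "This will allow us to detect a difference in rates of desensitisation of 50%, with 80% power using a two-sided significance level of 0.05". The same sentence claims that a loss of 30% of the children is already covered. The section names PASS 14 as the software but not the test that was used for sizing.

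Section 9.2.1 compares the proportions tolerating at least 4443 mg of egg protein "using a two-sided Fisher's exact test". Section 9.2 makes the primary analysis intention to treat: "all subjects allocated to each arm will be analysed together as representing that treatment arm". A per-protocol analysis is secondary. Section 3.5 says that drop-outs are not replaced.

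**The concern.** The power statement and the planned test have to belong together, and with 33 children the choice of test changes power a great deal. Fisher's exact test is conservative in samples this small: its maximum true size is 0.029 at 22/11 and 0.028 at 15/8, against a nominal 0.05. A figure from a normal approximation can therefore be far too optimistic for it.

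There is also a mismatch of analysis sets. Section 9.1 allows for children lost to attrition, while section 9.2 keeps every randomised child in the primary analysis. The plan does not say how a child without the exit challenge (T3) is counted, so the power of the intention-to-treat analysis cannot be read from 9.1.

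Section 9.1 is the only justification for the number of children. Ethics reviewers weigh it when they judge whether the exposure is warranted, and readers will weigh it when they interpret a non-significant result.

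**Working it through.** **Inputs, all from the plan.** Active rate 0.65, control rate 0.15, two-sided alpha 0.05, 22 + 11 randomised, 30% attrition (section 9.1); two-sided Fisher's exact test (section 9.2.1).

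**Step 1: children left after attrition.** 22 × 0.7 = 15.4 and 11 × 0.7 = 7.7. The nearest whole numbers are 15 and 8, total 23. In reverse, 23 / 0.7 = 32.9, which rounds up to 33.

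**Step 2: reproduce the plan's 80%.** The unpooled normal approximation is power = Φ(|p1 − p2| / SE − 1.96), with SE = √[p1(1 − p1)/n1 + p2(1 − p2)/n2].

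- At 15/8: SE = √(0.2275/15 + 0.1275/8) = 0.1764, and Φ(0.5/0.1764 − 1.96) = Φ(0.875) = 80.9%.
- At 15.4/7.7: 80.6%. At 15/7: 78.1%.

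This matches the stated figure after attrition. The pooled normal approximation does not: it gives 65.7% at 15/8. It does give 82.5% at 22/11, and 33 is also the total it requires for 80% power, but only with no allowance for attrition.

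**Step 3: power of the planned test.** Power = Σ Bin(a; n1, 0.65) × Bin(b; n2, 0.15), summed over every table (a, b) whose two-sided Fisher p-value is below 0.05.

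| Analysed (active/control) | Situation | Fisher power |
|---|---|---|
| 22/11 | all 33 analysed | 75.4% |
| 15/8 | 30% attrition, nearest rounding | 54.8% |
| 16/7 | total 23, other rounding | 49.4% |
| 16/8 | both rounded up | 59.2% |
| 15/7 | both rounded down | about 44% |
| 24/12 | smallest 2:1 design reaching 80% | 80.9% |

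The 36 evaluable children in the last row already exceed the 33 to be randomised, before any loss.

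**Step 4: intention to treat with drop-outs counted as failures.** This rule is an assumption; the plan gives none. If 65% and 15% are completer rates and 30% drop out of each arm, the rates become 0.65 × 0.7 = 45.5% and 0.15 × 0.7 = 10.5%. Fisher power at 22/11 is then 44.4%. If only the active arm is diluted (45.5% against 15%), it is 32.1%.

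**Step 5: sensitivity to the assumed rates.** Against a 15% control rate, 80% power needs an active rate of about 68% at 22/11 and about 76% at 15/8. If the 50-point difference is held and the control rate runs from 5% to 25%, power is 84% down to 71% at 22/11, and 51% to 60% at 15/8.

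**The case against.** The strongest reply is that the primary analysis is intention to treat, so 15/8 is closer to a completer set and is not the primary one. With all 33 analysed, and with 65% and 15% read as intention-to-treat rates, the shortfall is under 5 points. This stands as a reason to lead with 75% and to present 55% as the attrition case. It does not rescue the 80%. Section 9.1 itself brings in attrition, and on the all-analysed reading that allowance has no meaning.

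Second, both rates are given as approximate. At 22/11 a modestly higher active rate (about 68%) or a lower control rate (8%, with the difference kept at 50 points, gives 81%) would reach 80%. That is correct for 22/11, so the finding applies at the stated rates. It gives no help at 15/8, where power stays at or below 60% across that range.

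Third, the 44% to 59% range is generous. 15/7 leaves 22 children, a 33% loss, and 16/8 leaves 24, a 27% loss. Totals of 23 give 49% to 55%. This is fair, and 54.8% is the figure to use.

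Fourth, 80% is obtainable by a recognised formula, so this is a mismatch of methods and not a slip of arithmetic. That too is fair as a description, but the formula is not for the test the plan will run.

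Finally, the study is described as exploratory, and Fisher's test keeps the type I error below 5%. No analysis is invalid. The stated power is still wrong.

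**Conclusion.** The concern holds and must be corrected. At 65% against 15%, the planned test has 75.4% power with 22 and 11 analysed and 54.8% with 15 and 8, against the stated 80%. If the assumed effect is real, it would be missed about 25% of the time with no losses and about 45% of the time with the stated losses, not 20%.

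The 75% figure assumes that 65% and 15% are rates among all randomised children. The 55% figure assumes that children lost to attrition leave the comparison and that the rates apply to those who remain. The 44% and 32% figures rest on counting drop-outs as failures, which the plan does not specify. No reading at the stated rates reaches 80% with Fisher's test. The unpooled approximation as the source of the 80% is an inference and the conclusion does not depend on it.

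**What to change.** Rewrite the power statement in 9.1 for the test in 9.2.1 and name the analysis set. Suggested wording: *With 22 and 11 children analysed and true rates of 65% and 15%, a two-sided Fisher's exact test at 0.05 has about 75% power. With 30% attrition (15 and 8 evaluable) it has about 55%, and 80% power would then need an active rate of about 76%.* State in the same place whether 65% is meant for all randomised children or for completers. A sentence in 9.2 on how a child without a T3 challenge is counted would settle which figure applies to the primary analysis.

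N can stay at 33. The cost is a change of text and a less favourable stated power.

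Enlarging the trial is a separate choice and is not needed to correct the error. To keep 80% with Fisher's test after 30% attrition, 36 evaluable children are needed: 36 / 0.7 = 51.4, so 52 randomised, or 54 (36 + 18) for whole 2:1 arms. That is 21 more children than planned, at a single site expecting about 12 months of recruitment.

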9.2 Statistical and Analytical Plans

The primary analysis will be performed on an intention to treat basis: all subjects allocated to each arm will be analysed together as representing that treatment arm, irrespective of compliance and whether or not they have completed the prescribed regimen. A secondary

analysis will also be performed on a per protocol basis. Statistical analysis was performed using SAS software version 9.4 for Windows (Cary, NC: SAS Institute Inc.). Statistical significant is set at $p < 0.05$.

9.2.1 Analysis of Primary Outcome

The primary analysis will compare the proportion of subjects who can tolerate 4443mg or more of egg protein in the active and control groups, using a two-sided Fisher's exact test.

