4.1 Randomisation and Blinding

OIT outcomes have been reported to be affected by a range of variables, including age, baseline egg-specific IgE, baseline reaction threshold and the presence of asthma (10). It is therefore essential to maintain balance between treatment groups with respect to these predictors. However, stratified randomisation using several variables is not effective in small trials. Minimisation is a valid alternative to ordinary randomisation, and has the advantage that there will be only minor differences between groups in baseline variables which are used in the allocation process (11). With minimisation, the treatment allocated to the next participant enrolled in the trial depends on the characteristics of those participants already enrolled, with an element of weighted randomisation – typically 80% chance – of each participant getting the allocation that minimises any imbalance. Randomisation with 2:1 allocation ratio will be performed using an online free, open-source, desktop minimization program with a random element using a weighting probability of 0.8 (MinimPy Program 0.3).

Baseline variables included in the minimisation will be:

- Age (<5, \geq 5 years)
- Egg-specific serum IgE (<10 kU/L, \geq 10 kU/L)
- Asthma on inhaled corticosteroids (No, Yes)

This is an open label study and blinding will not be performed.

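### The primary Fisher test is conservative at 22 v 11 and leaves out the minimisation factors; a pre-specified adjusted Firth test holds its size and has more power, mostly from leaving Fisher

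*Combined protocol and SAP*

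**What the plan says.** Section 4.1 lists age, baseline egg-specific IgE, baseline reaction threshold and asthma as variables reported to affect oral immunotherapy outcomes. It adds: "It is therefore essential to maintain balance between treatment groups with respect to these predictors". Allocation is 2:1 by minimisation with a weighting probability of 0.8, on age (<5 or ≥5 years), egg-specific IgE (<10 or ≥10 kU/L) and asthma on inhaled corticosteroids (no or yes). Section 4.1 gives no odds ratio or prevalence for any of them, and nor does any other section.

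Section 9.2 states: "The primary analysis will be performed on an intention to treat basis". Section 9.2.1 compares the proportions tolerating 4443 mg "in the active and control groups, using a two-sided Fisher's exact test". No covariate enters the primary comparison, and no adjusted sensitivity analysis is planned. The only covariate model, in 9.2.2, is for adverse events.

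Section 9.1 assumes about 65% success on active and 15% on control, with children "randomised 2:1 to active (n=22) or control (n=11) groups". It says this will "detect a difference in rates of desensitisation of 50%, with 80% power using a two-sided significance level of 0.05", allowing for 30% attrition.

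**The concern.** The design treats three baseline factors as important enough to steer allocation, and the analysis then drops them. If they are prognostic, minimisation makes the arms more alike than simple randomisation would. A test that ignores this counts variation the design has removed as noise. Fisher's test is also discrete in a trial this small, so it cannot use its full 5%. Together these mean that a true effect of the planned size is missed more often than the same children's data require. With only 33 children, no replacement of dropouts (section 3.5) and 30% attrition expected, that loss matters. There is no risk of an excess of false positives.

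**Working it through.** **1. The plan's own figure.** Inputs from section 9.1: 65% v 15%, 2:1, two-sided 0.05, 80% power, 30% attrition. The unpooled normal formula gives, for the control arm,

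n = (1.960 + 0.842)² × [0.15×0.85 + (0.65×0.35)/2] / 0.50² = 7.849 × 0.24125 / 0.25 = 7.57.

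The total is 3 × 7.57 = 22.7, and 22.7 / 0.7 = 32.5, hence 33. So 33 is reproduced, but with a normal approximation and not with the Fisher test named in 9.2.1.

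**2. Exact power of Fisher at 22 v 11.** For each number of control successes, multiply its binomial probability (11 children, 15%) by the probability that the active arm (22 children, 65%) reaches the smallest count giving p < 0.05.

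| Control successes | Probability | Active successes needed | Probability reached | Product |
|---|---|---|---|---|
| 0 | 0.1673 | 8 | 0.9984 | 0.1671 |
| 1 | 0.3248 | 11 | 0.9526 | 0.3094 |
| 2 | 0.2866 | 13 | 0.7916 | 0.2269 |
| 3 | 0.1517 | 16 | 0.3022 | 0.0459 |
| 4 | 0.0536 | 18 | 0.0716 | 0.0038 |
| 5 or more | | | | 0.0010 |

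The sum is 0.754, so power is 75.4% with no attrition. The same calculation gives 55% at 15 v 8 and 59% at 16 v 8, the sizes closest to 33 × 0.7 = 23.1. If dropouts are instead kept and counted as failures (an assumption; the plan does not say), the rates become 0.65 × 0.7 = 45.5% and 0.15 × 0.7 = 10.5%, and power at 22 v 11 is 44%.

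**3. Why Fisher is conservative.** With no prognostic factor at all, its exact size at 22 v 11 is at most 2.9% over all common success rates. That is discreteness alone. With prognostic minimisation factors ignored, simulated size at a 50% null falls further, to about 1.4% at an odds ratio of 3 per factor. Discreteness is the main cause and ignoring the factors adds to it.

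**4. The adjusted alternative.** Simulated trials had 33 children, biased-coin minimisation holding about 2:1, and marginal rates of 65% and 15%. Assumed, because the documents are silent: prevalences of 50/40/25% and a common odds ratio (OR) of 1 to 4 per factor. One set of 2,000 trials per row (Monte Carlo standard error about 0.9 points) separates the two sources of gain:

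| OR per factor | Fisher | Firth, arm only | Firth, arm + 3 factors | Gain from leaving Fisher | Gain from adjusting |
|---|---|---|---|---|---|
| 1 | 75.3% | 81.8% | 81.7% | 6.5 | −0.1 |
| 2 | 76.2% | 81.4% | 83.3% | 5.2 | 1.9 |
| 3 | 75.8% | 82.2% | 87.1% | 6.4 | 4.9 |
| 4 | 76.1% | 81.9% | 87.1% | 5.8 | 5.2 |

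Further runs under the same assumptions gave 81/84/87/89% for adjusted Firth and 81–83% for unadjusted Firth. Across runs, leaving Fisher is worth about 5–7 points and adjusting about 0–7. Under nulls of 15%, 30% and 50%, the adjusted penalised likelihood-ratio test had size of about 3–5%. At most 2 of 3,000 fits failed in any scenario.

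**5. After attrition.** With 23 children left and OR 2, power rose from about 55% (Fisher) to 66% (adjusted Firth). All 11 points came from leaving Fisher.

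**6. Methods to avoid.** Ordinary logistic regression on the same four terms, simulated with assumed prevalences of 50/50/30% and OR 1–5, met sparse data or separation in about 18–38% of trials at the planned rates. Its likelihood-ratio test had size 7–10%. Its Wald test had only 53–64% power, against 76–77% for Fisher.

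**The case against.** Fisher's test is valid, needs no model and is easy to explain, which suits a small open-label trial. Its true error rate is below 5%, so it cannot manufacture a finding. That stands: this is a matter of efficiency, not an error.

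A reader might infer that Fisher is conservative because it ignores the minimisation factors, and that adjustment by itself would return 5 to 11 points at no cost. The documents do not support that. The size is already at most 2.9% with no prognostic factor in play, and Firth regression without covariates recovers about 5–7 points. Boschloo's exact test, also without covariates, reaches 79.5% with maximum size 4.1%. What adjustment adds depends on odds ratios and prevalences that section 4.1 does not give, and it is nil if the factors are not prognostic. The upper end needs odds ratios of 3–4 for all three factors at once.

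Nor is the change free of cost. About 0.15 × 11 = 1.65 control successes are expected, which is thin for a four-term model, and the choice of method matters (step 6). The penalised test did hold its size in these simulations.

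Finally, the loss of power from attrition is larger than anything the choice of test can recover. That also stands.

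**Conclusion.** The point holds as an improvement the sponsor should make. The primary test omits the factors used in allocation and is conservative at 22 v 11, mainly through discreteness. It has 75.4% power with complete data and about 55–59% after the planned attrition, not 80%. The adjusted Firth test reaches about 81–89% with 33 complete outcomes at a size of about 3–5%, given the assumed odds ratios and prevalences. The documents establish the omission and the exact Fisher figures; the share of the gain due to adjustment rests on those assumptions. After attrition, the one Firth scenario examined showed a useful gain of about 11 points, none of it from adjustment, and power was still well short of 80%.

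**What to change.** In section 9.2.1, before any outcomes are seen, name as the primary analysis a Firth penalised logistic regression of success at T3 on arm, age group, egg-specific IgE group and asthma on inhaled corticosteroids, with a two-sided penalised likelihood-ratio test for arm. Keep the two-sided Fisher test as a sensitivity analysis. State that ordinary logistic likelihood-ratio and Wald tests will not be used. If a standardised risk difference is reported, name its confidence interval method (for example, bootstrap) and call it supportive, because its coverage has not been checked here.

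The cost is a paragraph and a few lines of SAS. No new data are needed, since minimisation requires all three factors before allocation. The price is a less simple model resting on few control successes. Because the study is open label, the change should be dated and fixed before T3 results accumulate. Section 9.1 should also state the power of the test actually chosen, with and without attrition, since this change alone does not deliver the stated 80%.
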